### **9.3 Documentation of Pregnancy**

If a female subject becomes pregnant during the study, she will be withdrawn from the study, the reason recorded in OnCore, and the study Sponsor/Investigator ([name]) notified. The pregnancy will be reported to the IRB according to local institutional reporting guidelines.

Though the subject will be withdrawn from the study, permission to record survival data for the mother to the end of the pregnancy and of the baby at birth will be requested

**9.4 Required Reporting of Fred Hutchinson Cancer Research Center to UMN (IND Sponsor)**

Events during the study period meeting the definition of serious, regardless of attribution or expectedness must be reported within 24 hours of knowledge to the University of Minnesota Study Coordinator.

Any event meeting the definition of an early study stopping event per section 12.5 must be reported within 24 hours of knowledge to the University of Minnesota Study Coordinator.

The UMN Study Coordinator will facilitate reporting to the University Of Minnesota IRB, Masonic Cancer Center, and the FDA as required.

University of Minnesota (contact information on page 5) with follow-up reporting to MCC Study Coordinator using the Event Report found in OnCore.

In addition, Fred Hutchinson Cancer Research Center will be responsible for submitting reportable events to their institutional IRB and any other required local regulatory entities.

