**Event Attribution Categories:**

CTCAE does not define an AE as necessarily ‘caused by a therapeutic intervention. The clinical investigator must assign attribution for an adverse event after naming and grading of the event.

Attribution	Description
Unrelated	The AE is clearly NOT related to the intervention
Unlikely	The AE is doubtfully related to the intervention
Possible	The AE may be related to the intervention
Probable	The AE is likely related to the intervention
Definite	The AE is clearly related to the intervention

**Unexpected adverse event or unexpected suspected adverse reaction:** An adverse event or suspected adverse reaction is considered “unexpected” if it is not listed in the investigator brochure or is not listed at the specificity or severity that has been observed; or, if an investigator brochure is not required or available, is not consistent with the risk information described in the general investigational plan or elsewhere in the current application, as amended. Thus, adverse events that occur as part of the transplant or underlying disease are considered unexpected; however, they will not be reportable per section 9.4.

**Expedited (Rapid) Reporting:** Certain events may require rapid notification to entities providing patient safety oversight (e.g. IRB, FDA) as detailed in section 9.4.

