## 9.2 Documentation of Adverse Events

The goal of AE monitoring will be to focus on events that are related directly to study participation, not the transplant procedure or the disease under treatment unless study participation exacerbates the event. Due to the complex medical condition of the post-transplant patient, monitoring for adverse events will focus on events beginning with the 1st dose of pamidronate through the Day 360 visit.

For patients assigned to pamidronate, a toxicity assessment will be done in conjunction with each infusion (Day 90, 180, and 270) at the following time points:

- Prior to the pamidronate infusion - within 72 hours before the infusion
- 1 week (+/- 3 days) after each pamidronate infusion via telephone interview
- At any unplanned visit

At each of these time points the worst grade of the targeted toxicity since the previous assessment will be recorded in addition to any unexpected toxicities felt at least possibly related to pamidronate.

Of special concern are rare, but potentially serious risks associated with pamidronate which, if serious enough will lead to the discontinuation of the study drug per section 12.5. These targeted toxicities (based on CTCAE v4) will be collected on all patients (control and pamidronate) are:

- Anterior uveitis by subject's report (blurred vision, eye pain, redness, sensitivity to light, irregular pupil)
- Atrial fibrillation by the subject's report (palpitations, chest pain, shortness of breath)
- Osteonecrosis of the jaw by subject's report (jaw pain, swelling, redness, or other signs of infection in the gums, gums or sockets that don't heal after dental work, numbness or a heavy feeling in the jaw, draining of pus, visible bone in the mouth, roughness of the gums in a particular area) and/or physical examination at study visits.

All targeted toxicities, regardless of grade, and other events, grade 3 or greater that are felt at least possibly related to study treatment or cannot be explained by another cause (i.e. unexpected, not related to transplant, disease for which the transplant was done, underlying medical condition, etc.) will be recorded in OnCore for all patients.

After completion of the targeted toxicity form at day 360 formal collection of adverse events ends; however the sponsor/investigator must report upon knowledge any treatment related event meeting the expedited reporting criteria found in section 9.1 regardless of timing to pamidronate.

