## 9.5 UMN Required Reporting: FDA, IRB, and MCC's SAE Coordinator

Agency	Criteria for reporting	Timeframe	Form to Use	Submission address/ fax numbers	Copy to:
UMN IRB	Events requiring prompt reporting including, but not limited to unanticipated death of a locally enrolled subject(s); new or increased risk; any adverse event that require a change to the protocol or consent form or any protocol deviation that resulting in harm refer to http://www.research.umn.edu/irb/guidance/ae.html#.VC7xraI0-sh	Within 5 business days of event discovery	Report Form	[contact]	MCC SAE Coordinator [contact]
FDA	Unexpected and fatal or life threatening suspected adverse reaction	As soon as possible but no later than 7 Calendar-Day	FDA prefers MedWatch 3500a Form however use of the UMCC SAE form is acceptable	Submit as an amendment to IND  With copy to the affiliate PI	
	1) Serious and unexpected suspected adverse reaction or 2) increased occurrence of serious suspected adverse reactions over that listed in the protocol or investigator brochure or 3) findings from other sources (other studies, animal or in vitro testing)	As soon as possible but no later than 15 Calendar-Day			
	Note: Events due to the disease under treatment or the transplant will not require expedited reporting to the FDA for the purposes of this study				
MCC SAE Coordinator	Stopping Rule Event – any grade 4 or 5 study-related toxicity in the pamidronate group or in either group (pamidronate or control) grade 3 or higher of the following selected toxicities: uveitis, atrial fibrillation or osteonecrosis of the jaw (ONJ)	at time of form completion	Event Form	[contact]	n/a

In each IND safety report, the sponsor must identify all IND safety reports previously submitted to the FDA concerning a similar suspected adverse reaction and must analyze the significance of the suspected adverse reaction in light of the previous, similar reports.

The SAE Coordinator will provide the Cancer Center's Data and Safety Monitoring Council (DSMC) with the SAE in an appropriate format depending on the individual SAE (as reported or in a summary format).

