#### **10.4 Data and Safety Monitoring Plan (DSMP)**

The study's Data and Safety Monitoring Plan will be in compliance with the University of Minnesota Masonic Cancer Center's Data & Safety Monitoring Plan (DSMP), which can be accessed at <http://z.umn.edu/dmsp>.

For the purposes of data and safety monitoring, this study is classified as high risk (under a locally held IND). Therefore the following requirements will be fulfilled:

- The Masonic Cancer Center Data and Safety Monitoring Council (DSMC) will assess the study's progress at least quarterly.
- The S/I will comply with at least twice yearly monitoring of the project by the Masonic Cancer Center monitoring services.
- The S/I will oversee the submission of all reportable events per the definition of reportable in section 9.4 to the Masonic Cancer Center's SAE Coordinator, the University of Minnesota IRB, and the FDA.

In addition, at the time of the continuing review with the University of Minnesota IRB, a copy of the report with any attachments will be submitted to the Cancer Protocol Review Committee (CPRC).

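### The serious-event reporting sections contradict one another, and only the affiliate site has an explicit rule covering serious events of every cause

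*Combined protocol and SAP*

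**What the plan says.** All references are to the combined protocol and SAP.

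- **9.4**, headed as reporting from Fred Hutchinson to UMN: "Events during the study period meeting the definition of serious, regardless of attribution or expectedness must be reported within 24 hours of knowledge" to the UMN coordinator. UMN then helps with onward reporting to its IRB, cancer center and the FDA where required.
- **9.1**, on unexpected events: "adverse events that occur as part of the transplant or underlying disease are considered unexpected; however, they will not be reportable per section 9.4". The next definition describes expedited reporting to "entities providing patient safety oversight (e.g. IRB, FDA) as detailed in section 9.4".
- **10.4**: "The S/I will oversee the submission of all reportable events per the definition of reportable in section 9.4" to the SAE Coordinator, the UMN IRB and the FDA.
- **9.5**, the UMN table: the IRB row covers events needing prompt reporting, including unanticipated deaths of local subjects, with a copy to the SAE Coordinator. The FDA rows cover suspected adverse reactions, and a note exempts disease and transplant events from FDA expediting. The SAE Coordinator row lists stopping-rule events: "any grade 4 or 5 study-related toxicity in the pamidronate group", or grade 3 or higher uveitis, atrial fibrillation or osteonecrosis of the jaw in either group.
- **9.2**, for all patients: targeted toxicities of any grade are recorded, with "other events, grade 3 or greater that are felt at least possibly related to study treatment or cannot be explained by another cause". Other 9.2 entries also depend on a judgement of relatedness, to pamidronate, to supplementation or to study procedures.
- **10.2**: deaths are entered in OnCore.
- **12.3**: each site has its own randomisation schedule, in blocks of 2 and 4 within two age strata.

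**The concern.** There are two separate problems.

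First, the rules cannot all be obeyed. For a child at the affiliate admitted to hospital with a transplant complication, 9.4 requires a report within 24 hours and 9.1 says none is due under 9.4. Read literally, 10.4 would also send that event to the FDA, which 9.5 says does not need expedited notice.

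Second, all-cause serious events are assured for one site only. The recording rule that both sites share, in 9.2, asks whether an event might be due to study treatment or lacks another explanation. The trial is open-label, so that question is answered with the arm known. In transplanted children most serious events will have another available explanation. If pamidronate changed the rate of, say, severe infection, individual cases could be put down to the transplant and not recorded. The protection against that is an all-cause count compared with the randomised controls, and the text assures one only at the affiliate.

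**Working it through.** **1. Where the references to 9.4 should point.** No plan figure underlies this step; it is a reading of the text.

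| Place | What it expects 9.4 to contain | Where that content is |
|---|---|---|
| 9.1, unexpected events | A reporting rule that exempts transplant and disease events | Note in 9.5, limited to FDA expediting |
| 9.1, expedited reporting | IRB and FDA reporting | 9.5 |
| 10.4 | A definition of reportable for the SAE Coordinator, IRB and FDA | 9.5 |

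All three fit 9.5 and none fits 9.4, which is an affiliate-to-sponsor notice. A stale section number explains both conflicts.

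**2. Is there a UMN counterpart to 9.4?** 9.5 lists prompt IRB events, FDA suspected reactions and stopping-rule events. 9.1 has the sponsor evaluate any event thought serious, but for expedited reporting, which is not a rule to record it. 9.2 filters on relatedness. No section requires every serious event in a UMN patient to be recorded.

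**3. Does the gap between sites bias the arms?** Let p be the true serious-event risk, equal in both arms. Suppose the affiliate captures all events and UMN a fraction c, the same in both arms. The table in 12.1 gives 43 per site at Day 90, taken here as randomised.

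- Balanced within site (21.5 per arm on average): the expected observed risk is p(1 + c)/2 in each arm, a difference of 0.
- Worst imbalance under 12.3: 2 per stratum over two strata gives 4, or 3 when the site total is odd. With 23:20 at one site and 20:23 at the other, the unstratified difference is 3p(1 − c)/43. At c = 0 this is 1.4 points for p = 0.2, 2.8 for p = 0.4 and 4.2 for p = 0.6. Stratifying by site makes it 0.

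**4. What is lost in precision.** The 95% margin on the arm difference is 1.96 × √(2 × 0.2 × 0.8 / n), with an assumed 20% risk per arm.

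- Both sites, n = 43 per arm: 16.9 points.
- Affiliate only, n = 21.5 per arm: 23.9 points.
- Power at two-sided 5% for an assumed 20% against 40%: 53% with both sites, 29% with one.

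**5. What the 9.2 filter can do.** Suppose fractions a (pamidronate) and b (control) of serious events pass the filter at UMN, with equal true risk p. The false difference at UMN is p(a − b). For illustration, p = 0.5, a = 0.3 and b = 0.1 give 0.5 × 0.2 = 10 points. Pooled with an equal-sized affiliate that captures everything, this becomes 5 points. If a = b it is 0. The documents give no values for p, a or b.

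**6. Deaths.** From 12.1, 96 × 0.90 = 86.4 reach Day 90, and 86.4 × 0.20 = 17.3 die between Day 90 and Day 360, about 8.6 per site.

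**The case against.** The strongest reply is that 9.4 is a notification rule, not a recording rule. UMN holds the IND, so the affiliate must notify UMN and UMN need not notify itself. The recording rule is 9.2, and it is the same at both sites and in both arms. Section 12 plans no analysis of the 9.4 notices, so nothing planned mixes two definitions. The conflict between sections is a stale number, and 9.4 already limits onward reporting to what is required. 9.2 also states openly that monitoring is meant to focus on study-related events. Finally, 10.4 binds the trial to an institutional monitoring plan that is not in these documents and may require more.

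Much of this stands. The contradiction is easily cured, and the gap is in what the protocol assures, not proof that events would go unrecorded. But one definition in 9.2 does not give one standard in practice when it rests on attribution with the arm known. The reply also leaves no assured all-cause record for half the trial.

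A reader might go further and infer that serious events cannot be compared between arms. The documents do not support that: the difference in rules lies between sites, each site is randomised separately in small blocks, and a site-stratified or affiliate-only comparison remains valid. Nor should a reader infer that deaths or relapses would be lost. Deaths go into OnCore, survival is sought even after withdrawal (7.8), unanticipated UMN deaths are copied to the SAE Coordinator, and relapse is a named reason for stopping pamidronate (7.4.6). The control group is also used, since 12.5 compares three selected toxicities between arms.

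**Conclusion.** The point holds in two parts. Sections 9.1 and 9.4 conflict on whether serious transplant or disease events are reportable, and 10.4 conflicts with the 9.5 note; references that should read 9.5 are the probable cause. Separately, for about 43 of 86 randomised children, the text does not assure that a non-fatal serious event is recorded unless it is a targeted toxicity or passes a relatedness judgement made open-label.

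Pooled all-cause serious-event rates would be incomplete and defined differently at the two sites. The direct cost to an arm comparison is precision: about ±24 points against ±17, assuming a 20% risk per arm and equal numbers per site. Bias is possible only through arm-dependent judgement in the 9.2 data; the 10-point illustration rests on assumed values. The roughly 17 deaths expected after Day 90 are already captured and are not part of the gap.

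This should be corrected. It is more than clerical, because staff cannot follow all the reporting rules as written, but it does not threaten the primary analysis.

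**What to change.** 1. Point both 9.1 references and the 10.4 reference to 9.5. Keep the 9.5 note on FDA expediting, and make the 9.1 exemption no wider than that note.
2. State one recording rule: from randomisation through Day 360, every event meeting the 9.1 definition of serious is entered in OnCore, at both sites and in both arms, whatever its attribution.
3. Tabulate these events, with all-cause death, by arm and stratified by site, at the 6-monthly interim reviews in 12.5.
4. Leave the affiliate's existing notification to the sponsor before randomisation unchanged.

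The cost is amendment wording and more event forms at UMN after Day 90. No visits or tests are added.

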## 9.5 UMN Required Reporting: FDA, IRB, and MCC's SAE Coordinator

Agency	Criteria for reporting	Timeframe	Form to Use	Submission address/ fax numbers	Copy to:
UMN IRB	Events requiring prompt reporting including, but not limited to unanticipated death of a locally enrolled subject(s); new or increased risk; any adverse event that require a change to the protocol or consent form or any protocol deviation that resulting in harm refer to http://www.research.umn.edu/irb/guidance/ae.html#.VC7xraI0-sh	Within 5 business days of event discovery	Report Form	[contact]	MCC SAE Coordinator [contact]
FDA	Unexpected and fatal or life threatening suspected adverse reaction	As soon as possible but no later than 7 Calendar-Day	FDA prefers MedWatch 3500a Form however use of the UMCC SAE form is acceptable	Submit as an amendment to IND  With copy to the affiliate PI	
	1) Serious and unexpected suspected adverse reaction or 2) increased occurrence of serious suspected adverse reactions over that listed in the protocol or investigator brochure or 3) findings from other sources (other studies, animal or in vitro testing)	As soon as possible but no later than 15 Calendar-Day			
	Note: Events due to the disease under treatment or the transplant will not require expedited reporting to the FDA for the purposes of this study				
MCC SAE Coordinator	Stopping Rule Event – any grade 4 or 5 study-related toxicity in the pamidronate group or in either group (pamidronate or control) grade 3 or higher of the following selected toxicities: uveitis, atrial fibrillation or osteonecrosis of the jaw (ONJ)	at time of form completion	Event Form	[contact]	n/a

In each IND safety report, the sponsor must identify all IND safety reports previously submitted to the FDA concerning a similar suspected adverse reaction and must analyze the significance of the suspected adverse reaction in light of the previous, similar reports.

The SAE Coordinator will provide the Cancer Center's Data and Safety Monitoring Council (DSMC) with the SAE in an appropriate format depending on the individual SAE (as reported or in a summary format).

## **10 Study Status Updates, Data Collection and Monitoring**

### **10.1 Study Status Updates**

During the trial's period of active enrollment a weekly summary report will be generated from OnCore by the University of Minnesota summarizing enrollment and toxicity activity to date, as well as, any relevant clinical information. Sites will be expected to keep OnCore current to meet the demands of this real time summary reporting.

In addition, at least monthly teleconferences will be initially held between the PI ([name]), UMN study personnel, and key representatives of the affiliate site to discuss enrollment, treatment tolerability and toxicity, sample collection, as well as other relevant issues. Depending on the speed of enrollment and the level of patient issues, these teleconferences may be held more frequently or cancelled if there are no issues to discuss.

### **10.2 Data Management**

This study will report clinical data using The Online Enterprise Research Management Environment (OnCoreTM), a web based Oracle® database utilizing study specific electronic case report forms. Key study personnel are trained on the use of OnCore and will comply with protocol specific instructions embedded within the OnCore forms. Patient demographics, patient specific study treatment calendars, adverse events, reporting of deaths, and other information required for IND annual reporting will be placed in OnCore and other research databases maintained by MCC IT.

Subject questionnaire recording will be recorded in Oncore.

### **10.3 Data Capture Methods**

All data will be collected at the site level by trained research study staff or site principal investigators using medical record documents, interviews, self-report instruments, lab reports, treatment strategies, and all related reports of outcome evaluations. Data from records abstraction, interviews, and participant self-reports will be entered by the research coordinator or other trained study staff at each site first onto paper CRFs and then into a secure, password-protected online database (OnCore). Copies of these paper CRFs will be retained along with other source documents in a participant file.

Participant data will be entered from the paper CRFs into electronic case report forms (e-CRFs). Both the paper and the e-CRFs will be approved by the study's

Principal Investigator and the Biostatistician prior to release for use. The Study Coordinator or designee will be responsible for registering the patient into OnCore at time of study entry, completing e-CRFs based on the patient specific calendar, and updating the patient record until patient death or end of required study participation.

#### **10.4 Data and Safety Monitoring Plan (DSMP)**

The study's Data and Safety Monitoring Plan will be in compliance with the University of Minnesota Masonic Cancer Center's Data & Safety Monitoring Plan (DSMP), which can be accessed at <http://z.umn.edu/dmsp>.

For the purposes of data and safety monitoring, this study is classified as high risk (under a locally held IND). Therefore the following requirements will be fulfilled:

- The Masonic Cancer Center Data and Safety Monitoring Council (DSMC) will assess the study's progress at least quarterly.
- The S/I will comply with at least twice yearly monitoring of the project by the Masonic Cancer Center monitoring services.
- The S/I will oversee the submission of all reportable events per the definition of reportable in section 9.4 to the Masonic Cancer Center's SAE Coordinator, the University of Minnesota IRB, and the FDA.

In addition, at the time of the continuing review with the University of Minnesota IRB, a copy of the report with any attachments will be submitted to the Cancer Protocol Review Committee (CPRC).

#### **IND Annual Reports**

In accordance with regulation 21 CFR § 312.33, the IND sponsor ([name]) will submit a progress report annually. The report will be submitted within 60 days of the anniversary date that the IND went into effect.

#### **10.5 Affiliate Site Monitoring**

The PI ([name]) with the CTO has oversight responsibility for trial monitoring at affiliate sites. The affiliate site must self-monitor following the University of Minnesota Masonic Cancer Center Data and Safety Monitoring Plan (DSMP - <http://z.umn.edu/dmsp>) and the CTO Affiliate and Satellite Site Monitoring SOPs.

The investigator will permit study-related monitoring, audits, and inspections by the study's S/I and/or any designees, the local IRB, government regulatory bodies, and University of Minnesota compliance groups. The investigator will make available all study related documents (e.g. source documents, regulatory

documents, data collection instruments, study data, etc.). The investigator will ensure the capability for inspections of applicable study-related facilities (e.g. pharmacy, diagnostic laboratory, etc.) will be available for trial related monitoring, audits, or regulatory inspections.

